7.2. Efficacy Assessments

The study efficacy assessments, for each of the main objectives, are summarized below in [Table 4](#).

Table 4. Study Efficacy Assessments

Objective	Assessments
Primary – Efficacy	
	
 Clinical Global Impression Severity focused on Agitation/ Aggression (CGI-S A/A) Borderline Personality Disorder Checklist (BPDCL)
Secondary – Efficacy	
	
 Borderline Evaluation of Severity over Time (BEST) Beck Depression Inventory – II (BDI-II) State-Trait Anger Expression Inventory 2 (STAXI-2) State-Trait Anxiety Inventory (STAI)
Exploratory-Efficacy	
	
 Agitation-Aggression Psychiatric Inventory-Clinician Report (AAPI-CR) Brief Assessment of Cognition (BAC) Columbia-Suicide Severity Rating Scale (C-SSRS) Number of visits to healthcare services outside of the trial (primary care, mental health services and ER visits)

All efficacy assessments will be measured at each of the indicated visits shown in the Schedule of Assessments and Procedures ([Table 1](#)) and Section 7.7.

All scales and questionnaires will be administered in the local language. Only scales and questionnaires provided by the Sponsor that have been validated in the local language, to which they have been translated, will be used as primary and secondary endpoints in this study.

Raters will be trained and certified in all scales before rating patients. Training and certification process will be outlined in the training material. For each individual patient, the same certified rater should rate

the patient throughout the study. In case of unforeseen circumstances, certified back-up raters should be available throughout the study.

Performance-based Outcome (PerfO) measure

7.2.1. Brief Assessment of Cognition (BAC) Scale

The Brief Assessment of Cognition (BAC) is a performance-based outcome measure that directly assesses cognitive performance via verbal memory/learning, working memory, motor function, verbal fluency, speed of processing, and executive function tasks (Atkins *et al.*, 2017). An electronic tablet-based version of the BAC will be used in this study. The tablet BAC was developed to allow standardized presentation of task instructions and stimuli, audio-recording of responses, and automatized scoring and data management. The BAC provides a composite measure of cognition, as well as individual scores for each of the six tasks. It has demonstrated equivalence with the original pen-and-paper measure (Atkins *et al.*, 2017).

Patient-Reported Outcome (PROs) measures

7.2.2. Beck Depression Inventory – II (BDI-II)

The Beck Depression Inventory, Version 2 (BDI-II) is a widely used 21-item patient-reported outcome (PRO) assessing the severity of depressive symptoms (Beck *et al.*, 1996). The BDI-II was developed to correspond to the DSM-IV and includes items measuring cognitive, affective, somatic, and vegetative symptoms of depression. Each item is rated on a 4-point scale with scores ranging from 0 (not at all) to 3 (extreme) for the severity of each symptom over the past two weeks. The BDI-II has excellent psychometric properties and has been found to be sensitive to change in depression.

7.2.3. Borderline Personality Disorder Evaluation of Severity over Time (BEST)

The Borderline Personality Disorder Evaluation of Severity over Time (BEST) is a 15-item PRO developed to assess BPD symptom severity and adaptive coping responses (Pfohl *et al.*, 2009). The first 12 items are focused on thoughts, emotions and behaviors related to BPD and participants are asked to rate each one on a 1 - 5 scale. The last 3 items ask about how frequently each of the three adaptive coping skills are used on a scale from “Almost Always” (5) to “Almost Never” (1). This instrument has good test-retest reliability and excellent internal consistency. The scale also demonstrated excellent discriminant validity and sensitivity to clinical change occurring as early as week 4 of the study (Pfohl *et al.*, 2009).

7.2.4. Borderline Personality Disorder Checklist (BPDCL)

The Borderline Personality Disorder Checklist (BPDCL) is a DSM-IV-based PRO designed to assess the extent to which respondents have been bothered by a range of BPD symptoms, over the course of the past month. Responses to the 47-items range from “Not at All” (1) to “Extremely” (5). Validation studies have demonstrated that the BPDCL discriminates between individuals with and without a diagnosis of BPD, and that it is sensitive to change of BPD symptoms (Bloo *et al.*, 2017; Calvo *et al.*, 2018). Overall, the BPDCL has good-to-excellent internal consistency, as well as very good discriminant, convergent and construct validity. Finally, as the confirmatory factor analysis on the BPDCL supported a nine-factor model aligned with the DSM-IV (as well as now DSM-V) BPD Diagnostic criteria, construct validity has been firmly established.

7.2.5.State-Trait Anxiety Inventory (STAI)

The State-Trait Anxiety Inventory (STAI, forms Y-1 and Y-2) is a 40-item PRO designed to measure two types of anxiety: *state-anxiety*, or current state anxiety about an event, and *trait-anxiety*, or general anxiety level as a personal characteristic (Spielberger *et al.*, 1983). Form Y, the most commonly used version of the scale, has 20-items for assessing state anxiety (STAI Form Y-1) and 20-items for assessing trait anxiety (STAI Form Y-2). State anxiety items (item 1 to item 20) include statements such as, “I am tense; I am worried” and “I feel calm; I feel secure” that measure the respondent’s feeling in that moment. Trait anxiety items (item 21 to item 40) include statements such as, “I worry too much over something that really doesn’t matter” and “I am content; I am a steady person” that measure how the respondent “generally” feels. All items, in both Form Y-1 and Form Y-2, are rated on a 4-point scale, where state anxiety items assess intensity of current feeling from “not at all” to “very much so”, and trait anxiety items assess frequency of feeling in general from “almost never” to “almost always”, with higher scores indicating greater anxiety. High scores on the STAI instrument have been found to indicate the presence of an anxiety or a depressive disorder among older adults. Considerable evidence attests to the construct and concurrent validity of the scale (Spielberger, 1999).

7.2.6.State-Trait Anger Expression Inventory 2 (STAXI-2)

The State-Trait Anger Expression Inventory-2 (STAXI-2) is a 57-item PRO designed to measure the intensity and expression of anger as an emotional state (State Anger) and as a personality trait (Trait Anger). Items are scored on a 4-point scale ranging from “Not at All” to “Almost Always.” Responses are based on the intensity and frequency of anger as well as how it is expressed and controlled. Concurrent validity of this instrument is strong in both clinical and nonclinical samples (Spielberger, 1999). Importantly, psychiatric patients showed higher experience and expression of anger than the general population sample (Lievaert *et al.*, 2016).

Clinician Reported Outcome (ClinRO) measures

7.2.7.Clinical Global Impression

The Clinical Global Impression (CGI) is one of the most widely used assessment measures used in psychiatry (Guy, 1976). It was originally designed for use in NIMH-sponsored clinical trials as a brief, stand-alone assessment of the clinician’s view of patient global functioning before and after study treatment (Busner & Targum, 2007). The illness severity and improvement items are most often used (versus therapeutic response) in clinical and research settings, and the measure has proved to be a robust efficacy measure in clinical drug trials (Guy, 1976). The CGI was designed to be completed with the totality of the information on the patient (i.e., collateral information), and has been adapted for use across various psychiatric (e.g., Depression, Schizophrenia, Anxiety, Bi-Polar Disorder, Impulse) and non-psychiatric (e.g., Restless Leg Syndrome, Ulcerative Colitis, Migraine) disorders. According to Busner and Targum (2007), the CGI has extraordinary utility as it is applicable across all CNS disorders and can be used regardless of the condition, population, or drug. Altogether, CGI construct validity is firmly established given the measure is designed for a specific condition or symptom under examination (i.e., the construct), and utilized by trained clinicians considering the totality of the collateral patient information for the specific condition or symptom under investigation.

For PORTICO, the Clinical Global Impression of Severity will be used focusing specifically on Agitation/Aggression (CGI-S A/A). For the CGI-S A/A, the clinician is asked, “Considering your total clinical experience with this particular population, how agitated/aggressive (i.e., ill) is the patient at this time?” Responses are on a 1-7 scale with higher scores indicating more severe illness. The CGI-S A/A should be

assessed considering the totality of collected data during the visit, including PRO performance, responses to the other ClinROs and information gleaned while talking with the patient during the visit.

7.2.8. Agitation and Aggression Psychiatric Inventory-Clinician Report (AAPI-CR)

The Agitation and Aggression Psychiatric Inventory – Clinician Report (AAPI-CR) is an 11-item semi-structured interview format ClinRO measure that was developed in consultation with experts in the field of scale development and psychometric validation and BPD experts.

As a semi-structured interview, the AAPI-CR allows clinicians to interact with patients and clarify responses to determine the most accurate clinical rating for each of the Frequency and Severity topic area items. The eleven topic area items (in parentheses) and their respective interview questions were developed in alignment with DSM-5 diagnostic criteria for Anxiety Disorders (Anxiety), Attention-Deficit Hyperactivity Disorder (Attention/Distractedness), Depression (Depression), Bi-Polar Disorder (Mania), Posttraumatic Stress Disorder (Traumatic Experiences), Schizophrenia (Delusions and Hallucinations), as well as behavioral characteristics of Borderline Personality Disorder (Agitation, Aggression, Disinhibition/Impulsivity, and Irritable Mood or Behaviors) (American Psychiatric Association, 2013). Considering the semi-structured interview asks questions regarding DMS-V diagnostic criteria for various disorders, construct validity is inherent in the measure's design.

Although the AAPI-CR was designed to align with the DSM-V criteria for various disorders and the behavioral symptoms of BPD, it was not intended to be used as a diagnostic measure, but rather will be employed to objectively quantify patients' frequency of symptoms, as well as determine the severity of these symptoms.

The score for each of the eleven topic area items is calculated by multiplying the average Frequency x average Severity score. The 11-items of the AAPI-CR contribute to two primary subscales of the AAPI-CR, namely the Agitation & Aggression Subscale (AAPI-A/A Subscale) and the Psychiatric Subscale (AAPI-P Subscale). The AAPI-A/A Subscale contains 4-items: Agitation, Aggression, Disinhibition/Impulsivity and Irritable Moods and Behaviors, and the Psychiatric Subscale is comprised of 7-items: Anxiety, Attention/Distractedness, Delusions, Depression, Hallucinations, Mania, and Traumatic Experiences.

As designed, the AAPI-CR is employed in PORTICO as an objective and quantifiable baseline measurement of participants' agitation and aggression, as well as the severity of their other symptoms. The AAPI-CR was developed because there is not currently commonly accepted measure of agitation and aggression; though the most commonly used measures of agitation and aggression are the NPI and CMAI, which are not appropriate for BPD because they are designed for use in an elderly population with dementia (De Mauleon *et al.*, Poster presentation at CTAD, 2019; Sano *et al.*, 2018). The NPI Agitation/Aggression (NPI-A/A) Subscale is comprised of the four items (i.e., Agitation, Aggression, Disinhibition and Aberrant Motor Behaviors). The NPI A/A minimum possible score is 0 and maximum 48. A total score (i.e., Frequency x Severity) cutoff of 8 in one of these items has been leveraged in Alzheimer's Disease Agitation and Aggression clinical trials (Porsteinsson *et al.*, 2014; Soto *et al.*, 2014), which corresponds to approximately 17% (i.e., $8/48 = 16.67$) of the possible range of the total NPI A/A. The AAPI-A/A has a minimum score of 4 and a maximum of 100. Therefore, an AAPI-AA total score (i.e., Frequency x Severity) cutoff of >16 (i.e., $16/96 = 16.67$) and a severity of > 6 was selected for this trial to ensure enrollment of a sufficiently agitated and aggressive BPD population experiencing at least moderately distressing agitation/aggression.

7.2.9. Columbia Suicide Severity Rating Scale (C-SSRS)

The Columbia Suicide Severity Rating Scale (C-SSRS) is a ClinRO administered in a semi-structured interview format, designed to evaluate suicide risk by assessing and tracking suicidal ideation and

behavior (Posner *et al.*, 2011). The C-SSRS identifies specific behaviors which may be indicative of an individual's intent to complete suicide. The C-SSRS has five-questions addressing suicidal ideation, five-sub-questions assessing the intensity of ideation, and four-questions addressing suicidal behavior. The scale should be administered by a certified rater and all positive scores should receive a careful clinical review to determine if intervention is needed. This instrument demonstrated good convergent and divergent validity with other suicidal ideation and behavior scales and has high sensitivity and specificity for suicidal behavior classifications. Both the ideation and behavior subscales are sensitive to change over time. The intensity of ideation subscale demonstrated moderate to strong internal consistency (Posner *et al.*, 2011).

7.2.10. Number of visits to healthcare services outside of the trial

The use of health care resources, including all the participant visits to primary care, mental health and emergency care services, will be recorded at each study visit, starting at baseline as described in [Table 1](#) and Section 7.7. The number of visits to healthcare services outside of the trial (primary care, mental health services & ER visits) will be evaluated '*in the last month*' at Baseline Visit as well as at Visit 4, Visit 6 and Visit 8/EoS.

7.3. Safety Assessments

The following safety variables will be measured at all visits as shown in the Schedule of Assessments and Procedures ([Table 1](#)) and Section 7.7.

- Treatment emergent adverse events (TEAEs) and Serious TEAEs
- Use of concomitant medication
- Physical examination (including height (screening only) and body weight; body mass index will be calculated from these)
- Vital signs (systolic and diastolic blood pressure, pulse and body temperature, all supine after 5 min rest)
- ECG
- Clinical laboratory results: hematology - including platelets and biochemistry
- Columbia Suicide Severity Rating Scale (C SSRS)

7.3.1. Treatment emergent Adverse Events (TEAEs)

Adverse events (AEs) will be recorded during the study period from the signing of informed consent to the completion of the Follow-Up Visit.

Treatment emergent adverse events are defined as AEs that started after first intake of study drug. If no unambiguous assignment to treatment emergent is possible due to incomplete or missing dates, the AE will be considered as treatment emergent.

All information obtained on TEAEs will be displayed and tabulated by participant, treatment and dose (i.e. arm). Classification based in the Medical Dictionary for Regulatory Activities (MedDRA latest version available) by System Organ Class (SOC), Preferred Term (PT) and Low-Level Term (LLT) will also be provided.

For further information of definitions and reporting of AEs and SAEs, see Section 8.2.

7.3.2. Physical Examination

All participants will undergo a standard physical examination including the evaluation of general appearance, eyes, throat-nose-ears, teeth, skin, lung, and heart. A general examination of abdomen, liver, spleen, kidneys, spine, lymph nodes, extremities and a short neurological status will also be performed.

The observed values will be recorded and assessed as “normal” or “abnormal”. Abnormal findings will be assessed as “clinically significant” or “not clinically significant”. All occurring abnormalities will be displayed by participant number.

An asymptomatic abnormal physical examination finding should only be reported as an AE if it is clinically significant, if it fulfils the criteria for an SAE, or if it causes the participant to discontinue the study.

If an abnormal physical examination finding is associated with clinical signs and symptoms, the sign/symptom should be reported as an AE and the associated physical examination finding should be considered additional information.

In addition to the physical examination described above, height (at screening only) and body weight will be measured at each visit.

The timing of the assessments is described in [Table 1](#) and Section 7.7.

7.3.3. Vital Signs

The following vital signs will be monitored as safety variables:

- Supine diastolic and systolic blood pressure (mmHg), after 5 minutes sitting down
- Supine heart rate (beats per minute), after 5 minutes sitting down
- Digital axillary or oral temperature (°C)

The observed values will be recorded and assessed as “normal” or “abnormal”. Abnormal findings will be assessed as “clinically significant” or “not clinically significant”. All occurring abnormalities will be displayed by participant number.

An asymptomatic abnormal vital sign finding must only be reported as an AE if it is clinically significant, if it fulfils the criteria for an SAE, or if it causes the participant to discontinue the study.

If an abnormal vital sign value is associated with clinical signs and symptoms, the sign/symptom should be reported as an AE and the associated vital sign result should be considered additional information.

Vital signs will be measured in all the study visits as described in [Table 1](#) and Section 7.7.

7.3.4. Electrocardiogram

A standard 12-lead ECG recording will be performed locally, at the clinical sites, including the parameters Heart Rate (HR), PR, QRS, QT and QTc. However, ECGs will be interpreted at a central reading center. Description of ECG intervals will be obtained and tabulated. All occurring abnormalities will be identified.

ECG parameters will be measured at Visit 1 and Visit 8 (EoS) as described in [Table 1](#) and Section 7.7.

7.3.5. Laboratory Safety Assessments

A maximum of 20 mL blood sample will be collected under fasting conditions at each visit. However, if the study visit is scheduled in the afternoon/evening, fasting conditions will only be required at Visit 2 (Baseline – Day 1), Visit 4 (Day 29), Visit 6 (Day 57) and Visit 8 (Day 85). Fasting conditions should last 6-8 hours before blood sampling.

Blood samples will be collected prior to study drug intake at all study visits as shown in the Schedule of Assessments and Procedures (Table 1) and Section 7.7.

At all study visits, the participant will be provided a snack/meal before completing the COAs.

The blood sampling and handling procedures are described in the study-specific Laboratory Specification Manual.

All blood samples for the laboratory safety assessments will be analyzed by a central laboratory. Urine drug screening and pregnancy test will also be analyzed at a central laboratory.

Laboratory kits for biological sampling (blood and urine) will be supplied by a central laboratory.

The different laboratory safety parameters to be measured are listed below in Table 5.

Table 5. Laboratory – Safety

Hematology Parameters (2 mL blood sample, potassium EDTA tube)	
White blood cell (WBC) count	Neutrophils absolute and %
Red blood cell (RBC) count	Lymphocytes absolute and %
Hemoglobin (Hb)	Monocytes absolute and %
Hematocrit (HCT)	Eosinophils absolute and %
Mean corpuscular volume (MCV)	Basophils absolute and %
Mean corpuscular hemoglobin (MCH)	Platelet count
Mean corpuscular hemoglobin concentration (MCHC)	
Serum Biochemistry Parameters (8.5 mL blood sample, Serum Separator Tube [SST])	
Sodium	Alkaline phosphatase (ALP)
Potassium	ALT
Calcium	AST
Urea	Creatine kinase (CK)
Creatinine	Gamma glutamyl transpeptidase (GGT)
Albumin	Lactate dehydrogenase (LDH)
Phosphate	Total Bilirubin
Glucose	Cholesterol
Triglycerides	Conjugated bilirubin
C-reactive protein (CRP)	Unconjugated bilirubin
Total Protein	Amylase
HbA1c*	TSH†
Serological Parameters (3.5 mL blood sample) †	

Hepatitis B Virus (HBV) Human Immunodeficiency Virus (HIV)	Hepatitis C Virus (HCV)
Urine Parameters	
Pregnancy test (and Serum human Chorionic Gonadotropin (S-hCG) in case of a positive result) ⁽¹⁾	
Drug screening	

* Only at the screening visit for diabetic participants

† Only at the screening visit, in case of serology confirmation an extra 8.5ml sample will be analyzed

⁽¹⁾ All positive urine pregnancy test results must be confirmed by a serum hCG test

Study medication must be halted in all patients who fail to have platelet counts checked at the scheduled timepoints. The study medication should not be resumed until testing has been completed and confirmed to be within an acceptable range.

At the discretion of the PI, additional and repeat testing may be performed in scheduled visits as well as in unscheduled safety visits.

Clinically significant out-of-range values must be recorded as an adverse event on an AE Form or as a serious adverse event (SAE) on a SAE form, if applicable.

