- (9) Blood extractions should ideally take place at the same time of the day and in fasting conditions (e.g., preferably, first thing in the morning) in order to allow participants to ingest food before going on with the rest of study assessments. In case the study visit is scheduled in the afternoon/evening, fasting conditions will only be required at Visit 2 (Baseline), Visit 4, Visit 6 and Visit 8. Fasting conditions should last 6-8 hours. All blood samples will be collected prior to study drug intake at all study visits.
- (9i) For US Sites ONLY: C_{max} will be assessed in a subset of participants. In these participants, one extra blood sample for PK assessments will be obtained 1 to 2 hours after IMP intake on Visits 4 and 6 (in addition to the pre-dose sample already scheduled on these visits). Participants will have to sign a separate specific informed consent form.
- (10) As blood sampling for the exploratory assessments is an integral part of the study, the main Patient Information Sheet covers these analyses
- (11) Study treatment will be dispensed at each study visit from Visit 2 to Visit 8. Each dispensation will consist in a box containing the treatment for 14 ± 2 days. At each visit, the first study drug intake, corresponding to the new treatment box dispensed on that visit, should occur at the clinic in fasting conditions, however If the study visit is scheduled in the afternoon/evening, no fasting conditions are required before IMP intake at the clinic .
- (12) ONLY APPLICABLE IN CASE THE PARTICIPANT IS RECEIVING CONCOMITANT TREATMENT WITH ANTIDEPRESSANTS (i.e., selective serotonin reuptake inhibitors, serotonin-norepinephrine reuptake inhibitors, tricyclics, tetracyclics, and triazolopyridines): A follow-up call will be required approximately 6-8 hours post first IMP administration, as well as at 24 hours and 48 hours to ensure participants are not experiencing any signs or symptoms of serotonin syndrome. If a participant is experiencing moderate symptoms of serotonin toxicity such as agitation, tachycardia, diaphoresis, and/or hyperthermia, then they will immediately be referred to local emergency services.

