7.7.2. Visit 2 (Week 0, Day 1) - Baseline Visit

Only participants who fulfil all eligibility criteria (Section 4.1) and have been given approval by Sponsor will be randomized to the study. At Visit 2, the following activities and assessments will be performed:

Prior to Randomization

- Verification of inclusion and exclusion criteria
- Physical examination (including weight)

- Changes in concomitant medication since the last visit
- Vital signs
- Blood extraction under fasting conditions for laboratory safety assessment: hematology and biochemistry
- Blood extraction under fasting conditions for PK assessments before the IMP intake
- Blood extraction under fasting conditions for LSD1-TE assessments before the IMP intake
- Blood extraction for genotyping. The blood sample could be obtained at any visit from Baseline Visit to the end of the study, however, baseline collection is recommended
- Blood extraction under fasting conditions for future investigations
- Urine pregnancy test (females of reproductive age)
- Urine drug screening

Randomization

- Adverse Events assessment
- Number of visits to healthcare services outside of the trial in the last month
- Dispensation of IMP and intake of the first capsule in fasting conditions
- Provide snack/meal
- COAs

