7.7.3. Visit 3 (Week 2, Day 15±2)

At Visit 3, the following activities and assessments will be performed:

- Adverse Events assessment
- Physical examination (including weight)
- Changes in concomitant medication since the last visit
- Vital signs
- Blood extraction under fasting conditions for laboratory safety assessment: hematology (including platelets) and biochemistry. If the study visit is scheduled in the afternoon/evening, fasting conditions will not be required.
- Urine drug screening
- Assess IMP compliance
- Dispensation of IMP and intake in fasting conditions of the first capsule from the new treatment box dispensed at this visit. If the study visit is scheduled in the afternoon/evening, fasting conditions will not be required.
- Provide snack/meal
- COAs (Note: for the STAI, Form Y-1 only)

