5.2.4 Clinical Laboratory Evaluation

For summaries by visit, the last non-missing assessment (including repeat assessments) recorded at each visit will be summarized. Unscheduled and unplanned assessments will be listed, but not included in by-visit summaries.

For across visit summaries (e.g., maximum post-baseline value), scheduled, unscheduled and repeat assessments will be considered.

A subject will be defined as having a treatment-emergent laboratory abnormality if the subject had a normal baseline value and an abnormal post-treatment start value.

The following summaries will be provided for each laboratory category:

- A summary of each laboratory parameters (absolute values and change from baseline) by treatment and visit
- A summary of the number and percentage of patients experiencing treatment emergent laboratory abnormalities by parameter, visit (and overall, throughout the study)
- A shift from baseline table by visit

Laboratory values for hematology, serum biochemistry, serological parameters and urine parameters will each be listed by subject and study time point including changes from baseline (with the exception of serological and urine parameters). The baseline for the laboratory values will be the last results obtained prior to treatment (Day 1 according to schedule)

All values outside the clinical reference ranges will be flagged in the data listings. The abnormal values will be flagged with 'L' for values below the lower limit of the clinical reference range and 'H' for values above the upper limit of the clinical reference range and included in the listings. The Investigator will assess whether the values outside the clinical reference range are clinically significant. Clinically significant laboratory values will be recorded by the Investigator as AEs.

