 - ii. If the subject withdraws consent during a visit but agrees to complete the visit, then, the investigator will complete an EoS Visit. All the data collected up to and including this visit will be used in the analysis.
 - iii. If the subject withdraws consent and refuses to complete the EoS Visit, no new information will be collected. However, it is recommended,

[figure not shown]
outside the scope of this study, to perform a safety assessment within 2 weeks after treatment discontinuation.

[figure not shown]
- (3) Informed consent at the Screening visit must be obtained before any study specific procedure.
- (4) Participant eligibility should be documented in a Subject Eligibility Form and submitted to the study medical monitor immediately after Visit 1 for approval before Visit 2.
- (5) Not applicable for non-completers (i.e.: subjects who received at least one dose of study treatment but prematurely discontinue the study before its completion).
- (6) The full State-Trait Anxiety Inventory (STAI) (Forms Y-1 & Y-2) will only be administered at Screening (Visit 1), Baseline (Visit 2) and Visit 8/EoS, whereas Form Y-1 ("state" anxiety) will be administered at all other visits.
- (7) The number of visits to healthcare services outside of the trial (primary care, mental health services & ER visits) will be evaluated 'in the last month' at Baseline and at Visit 4, Visit 6 and Visit 8/EoS.
- (8) Vital signs and electrocardiogram (ECG) should be obtained for a subject in the same manner throughout the study (e.g., obtained from the same arm).
- (9) Blood extractions should take place at the same time of the day and in fasting conditions (first thing in the morning preferably, in order to allow subjects to ingest food before going on with the rest of the study assessments). In case the study visit is scheduled in the afternoon, fasting conditions should last 6-8 hours. Subjects should be instructed to take IMP in fasting conditions.
- (9i) For US Sites ONLY: Cmax will be assessed in a subset of subjects. In these subjects, one extra blood sample for PK assessments will be obtained 1 to 2 hours after IMP intake on Visits 4 and 6 (in addition to the pre-dose sample already scheduled on these visits). Subjects will have to sign a separate specific informed consent form.
- (10) As blood sampling for the exploratory assessments is an integral part of the study, the main Patient Information Sheet covers these analyses

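### Glucose and triglycerides may be fed samples at four of seven post-baseline visits, but SAP 5.2.4 compares every visit with a fasting Day 1 baseline and ignores fasting status

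*Protocol*

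**What the plan says.** **Sampling rule.** Protocol 7.3.5 sets fasting as the default at each visit and then makes an exception: "if the study visit is scheduled in the afternoon/evening, fasting conditions will only be required at Visit 2", with Visits 4, 6 and 8 named next. Footnote 9 to Table 1 agrees: "fasting conditions will only be required at Visit 2 (Baseline), Visit 4, Visit 6 and Visit 8". The visit descriptions in 7.7.3, 7.7.5, 7.7.7 and 7.7.9 repeat the waiver beside the safety blood draw. At Visit 3, for example: "If the study visit is scheduled in the afternoon/evening, fasting conditions will not be required". Visit 2 has no waiver; section 7.7.2 lists "Blood extraction under fasting conditions for laboratory safety assessment: hematology and biochemistry".

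**Analytes.** Protocol Table 5 puts glucose and triglycerides in the biochemistry panel. Table 1 schedules that panel at every visit.

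**Analysis.** SAP 5.2.4 takes the last pre-treatment result, Day 1 by schedule, as the laboratory baseline. It plans "A summary of each laboratory parameters (absolute values and change from baseline) by treatment and visit", a shift table by visit, and counts of treatment-emergent abnormalities by visit and for the whole study. A participant has such an abnormality "if the subject had a normal baseline value and an abnormal post-treatment start value". Across-visit summaries, such as the highest post-baseline value, also draw on unscheduled and repeat samples. Nothing in the section depends on fasting status.

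**SAP schedule.** Footnote 9 in SAP 7.1 does not carry the waiver. It asks for fasting samples and adds "In case the study visit is scheduled in the afternoon, fasting conditions should last 6-8 hours", without limiting this to certain visits.

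**The concern.** Glucose and triglycerides are the two analytes in the panel considered here as responding to a recent meal. If the baseline is fasting and a later sample is not, part of the change may reflect food and not treatment. The SAP's definition of treatment-emergent needs only a normal baseline and one later out-of-range value, so a single post-meal result is enough.

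The outputs at stake are descriptive safety tables. The whole-study count and the across-visit maximum would pool samples taken under two conditions, and a reader of those tables could not separate them. The by-visit means could also alternate, with mixed samples at Visits 3, 5, 7 and 9 and fasting samples at Visits 4, 6 and 8. The SAP's own schedule suggests that it was not aligned with the protocol's fasting text.

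**Working it through.** The plan states no figure on this point, so there is none to reproduce. The check sets the passages side by side and then gives an illustration on assumed rates.

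**1. Visits.** Post-baseline laboratory visits are Visits 3 to 9, seven in all (protocol Table 1). Afternoon fasting is waived at four (3, 5, 7, 9) and required at three (4, 6, 8). Visit 9 follows two weeks on placebo in both arms, and its laboratory draw does not apply to non-completers.

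**2. Outputs in SAP 5.2.4, for glucose and triglycerides.**

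| Output | What is compared | Affected? |
|---|---|---|
| By-visit tables, Visits 4, 6, 8 | fasting with fasting | No |
| By-visit tables, Visits 3, 5, 7, 9 | mix of fed and fasting with fasting | Yes |
| Whole-study treatment-emergent count | all seven visits pooled | Yes |
| Across-visit maximum | all visits pooled, plus unscheduled and repeat samples | Yes |

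**3. Illustration for one analyte.** Let q0 be the chance of an out-of-range value at a fasting visit and q1 the chance at a fed visit, both among participants with a normal Day 1 value. Take visits as independent. None of these inputs is in the documents.

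- All seven visits fasting: 1 − (1 − q0)^7
- Participant seen in the afternoon, fed at Visits 3, 5, 7 and 9: 1 − (1 − q0)^3 × (1 − q1)^4
- Arm with a share s of such participants: (1 − s) × first + s × second

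With q0 = 2%, the first is 1 − 0.98^7 = 13.2%. With q1 = 10%, the second is 1 − 0.98^3 × 0.90^4 = 38.2%. At s = 50%, the arm figure is 0.5 × 13.2% + 0.5 × 38.2% = 25.7%.

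| q1 (q0 = 2%) | All fasting | s = 25% | s = 50% | s = 100% |
|---|---|---|---|---|
| 5% | 13.2% | 15.7% | 18.3% | 23.3% |
| 10% | 13.2% | 19.5% | 25.7% | 38.2% |
| 20% | 13.2% | 25.3% | 37.3% | 61.4% |

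Over q0 of 1% to 5% and q1 of 5% to 20%, with q1 above q0, the all-fasting figure runs from 6.8% to 30.2% and the all-afternoon figure from 21.0% to 64.9%. Abnormal values cluster within a participant, which would lower every at-least-one figure.

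**4. Effect on the comparison.** Both arms follow the same sampling rule, so the background proportion b is expected to rise equally. If the drug adds an assumed risk d = 12% among participants not otherwise abnormal, the difference between arms is d × (1 − b). At b = 13.2% that is 0.12 × 0.868 = 10.4 percentage points; at b = 38.2% it is 0.12 × 0.618 = 7.4 points. The difference shrinks but keeps its sign.

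**The case against.** The strongest reply is that the exposure is narrow. Fasting is the protocol's default, and 7.7 prefers early-morning visits, so fed samples may be few. The by-visit tables already give three clean fasting comparisons, including Visit 8 at the end of treatment. SAP 5.2.4 plans no test on laboratory data. Investigators judge the clinical significance of out-of-range values, and protocol 9.3.6 grades shifts on that judgement. Nothing in the programme points to glucose or lipids: Phase I biochemistry appeared stable (protocol 1.4.1), and the events of special interest are platelet and neutrophil decreases. The laboratory manual or eCRF may also record fasting status; neither is available here.

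Most of this stands, and it rules out several stronger conclusions that a reader might draw:

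- *Every fed value counts as treatment-emergent.* It does not. The value must be out of range and the Day 1 value normal.
- *The tables are biased against the drug.* The same rule applies to both randomised, blinded arms, so the fed share is expected to be equal.
- *A real metabolic effect would be hidden.* The Visit 4, 6 and 8 tables would still show it.
- *The declared endpoint on laboratory values of potential clinical concern is inflated.* The documents do not equate that endpoint with any out-of-range value.

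What the reply does not remove is the pooling in the whole-study count and the across-visit maximum. Investigator review limits spill-over into adverse events, but the SAP's treatment-emergent definition does not use it. Even if fasting status is recorded, SAP 5.2.4 does not use that either.

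**Conclusion.** The mismatch holds, as a minor point. Followed as written, SAP 5.2.4 can mix fed and fasting glucose and triglyceride values in the whole-study treatment-emergent count, in the across-visit maximum, and in the by-visit tables for Visits 3, 5, 7 and 9. The expected consequence is a higher background in both arms and a diluted contrast, with no shift towards either arm.

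The size cannot be determined from the documents. It depends on the share of afternoon visits, the fasting and fed abnormal rates, how far abnormal values cluster within participants, and whether the central laboratory's reference ranges are fasting ranges. None of these is given, so the percentages in the illustration show direction and sensitivity and are not estimates for this trial.

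The conclusion also assumes that baseline is the Visit 2 sample. If that result is missing and screening is used instead, the baseline may itself be fed, because 7.7.1 waives afternoon fasting at screening too.

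**What to change.** In SAP 5.2.4, for glucose and triglycerides only:

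- Keep the all-visit tables as planned.
- Add the whole-study treatment-emergent count and the across-visit maximum for fasting samples only. Use samples recorded as fasting if that status is captured; otherwise use Visits 4, 6 and 8.
- Footnote the Visit 3, 5, 7 and 9 summaries as possibly non-fasting.

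Reconcile footnote 9 in SAP 7.1 with the protocol's fasting text.

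Restricting all tables for these analytes to Visits 2, 4, 6 and 8 would be a poorer choice. It would drop properly fasted morning samples, and the earliest on-treatment values at Visit 3, from the summaries.

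The cost is a few extra table rows, and fewer time points in the fasting-only summary (three post-baseline visits instead of seven if fasting status is not recorded). Sampling and visit procedures do not change.
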